#### **3.5.1 *Outcome/Endpoint Variables - Scoring of PRO Questionnaires***

##### **Health Assessment Questionnaire Disability Index (HAQ DI)**

In the HAQ DI, each category contains four response options ranging from 0-3, where 0 = without any difficulty and 3 = unable to do. In any event, a patient must have a score for at least six of the eight categories (i.e. Dressing and grooming, arising, eating, walking, hygiene, reach, grip, and activities). The HAQ DI's scoring conventions allow for the computation of two disability indices:

1. Standard HAQ DI (preferred and traditional scoring method; takes into account the use of aids/devices)

There are three steps:

- 1) Sum the 8 category scores by using the highest sub-category score from each category.
  - For example, there are three sub-category items in “Eating”. A patient responds with a 1, 2, and 0, respectively; thus, the category score is 2.
- 2) Adjust for use of aids/devices and/or help from another person when indicated.
  - Adjust the score for a category by increasing a 0 or 1 to a 2.
  - If the patient’s highest score is a 2, it would remain as 2.
- 3) Divide the summed category scores by the number of categories answered to obtain a HAQ DI score of 0-3 (3=worst functioning).

2. Alternative HAQ DI Score (without aids/devices)

There are two steps:

- 1) Sum the scores for each category, ignoring scoring for aids/devices
- 2) Divide by the number of categories answered (minimum 6 required). This yields a score of 0-3 (3=worst functioning).

### **Short Form (36) Health Survey (SF-36)**

SF-36 scoring will be conducted by following these 7 steps in accordance to the developer’s recommendations:

#### **Step 1: Data entry**

SF-36 scoring must ensure that the survey form is complete and the respondent’s answers are unambiguous. If there are missing responses, using a scoring algorithm could derive scores across the eight SF-36 health domain scales for nearly all survey respondents. If there are multiple responses for a single item, the following rules are applied:

1. If a respondent marks two responses that are adjacent to each other, randomly pick one, and enter that number.
2. If a respondent marks two responses that are not adjacent to each other, consider that item missing.
3. If a respondent marks three or more responses, consider that item missing.

Alternatively, one can opt to treat all items with more than one response as missing.

#### **Step 2: Recoding item response values**

This is a process that derives the final item response values, or scores, to be used when calculating the raw scale scores for each health domain.

#### **Step 3: Determining the health domain scale total raw scores**

Following item recording, which includes resolving items with missing data, a total raw score is computed for each health domain scale. The total raw score is the simple algebraic sum of the final response values for all the values for all the items in a given scale. The simple scoring method is possible because all the items in a given scale

have roughly equivalent relationships to the underlying health construct being measured and because no item is used on more than one scale. As a result, it is not necessary to standardize or weight items.

#### **Step 4: Transforming health domain scale total raw scores to 0-100 scores**

Health domain scale total raw scores are converted to 0-100 scores using the following formula:

$$\text{Transformed scale score} = \frac{(\text{Actual raw score} - \text{Lowest possible raw score})}{\text{Possible raw score range}} \times 100$$

#### **Step 5: Transforming health domain scale 0-100 scores to T scores using health domain z scores**

The advantages of standardizing the health domain scales and converting 0-100 scores to norm-based scores using a T-score transformation are that health domain scale results can be meaningfully compared with each other and that these scores have a direct interpretation in relation to the distribution of scores in the 2009 US general population.

The first step is to convert the 0-100 scores into a linear z-score. A z-score would ensure each health domain scale has a mean of 0 and a standard deviation of 1 in the 2009 US general population. A z-score is computed by subtracting each health domain scale's 2009 US general population mean from the 0-100 score for that scale, and dividing the difference by the given scale's standard deviation. Thus, the following formula is applied to convert 0-100 scores into z-scores:

$$\text{z-score} = \frac{([\text{0-100 score}] - [83.29094])}{(23.75883)}$$

Z-scores are then transformed into T-scores (mean = 50, SD = 10) using the following formula:

$$\text{T-Score} = 50 + (\text{z-score} \times 10)$$

#### **Step 6: Scoring the physical and mental component summary measures using health domain z scores**

The Physical Component Summary (PCS) and Mental Component Summary (MCS) measures are then scored using a three-step procedure, regardless of whether a standard or acute form was administered. First, the eight health domain scales are standardized using means and standard deviations from the 2009 U.S. general population. Second, these standardized scores are aggregated using weights (factor score coefficients) from the 1990 US general population. Computation of an aggregate physical component score consists

of multiplying each health domain scale z-score by its respective physical factor score coefficient and then summing the eight products. Similarly, an aggregate mental component score is obtained by multiplying each health domain scale z-score by its respective mental factor score coefficient and summing the eight products. To illustrate, a portion of the formula for aggregating scales when estimating a standard form of aggregate mental component score is as follows:

$$\begin{aligned} \text{Aggregate mental component score} = \\ (\text{PF z-score} \times -0.22999) \dots + (\text{MH z-score} \times 0.48581) \end{aligned}$$

Third, aggregate PCS and MCS scores are standardized using a linear T-score transformation with a mean of 50 and a standard deviation of 10. The formulas for computing the norm-based T score for each component summary measure are:

$$\begin{aligned} \text{PCS T-score} &= 50 + (\text{Aggregate physical component score} \times 10) \\ \text{MCS T-score} &= 50 + (\text{Aggregate mental component score} \times 10) \end{aligned}$$

#### **Step 7: Scoring the response consistency index (RCI)**

The Response Consistency Index (RCI) is optional, but is a simple and easy way to evaluate the consistency of responses to individual survey items. The RCI comprises of 15 pairs of items and assesses each pair for consistency. If a pair of responses is consistent, then the RCI score for that pair would be 0. Conversely, a pair of inconsistent responses would earn a score of 1. For example, if a respondent indicates that he or she can “walk more than a mile” but, at the same time, cannot “walk 100 yards,” then this item pair would be considered inconsistent and would earn 1 RCI point. For a given respondent, the final RCI score is the sum of the scores earned on the 15 consistency checks. Thus, the best (i.e., most consistent) RCI score is 0 and the worst (i.e., least consistent) score is 15. Note that it is not necessary for a respondent to have complete data for all 15 pairs to compute the RCI (pairs with missing or out-of-range data are not used in the final calculation). However, if all 15 pairs have missing data for one or both items, then the RCI for that respondent cannot be scored.

### **EuroQol 5 dimension, 3 level quality of life questionnaire (EQ-5D-3L)**

The EQ-5D-3L questionnaire is made up for two components; health state description and evaluation.

As to the health state description, the EQ-5D-3L descriptive system contains 5 categories (mobility, self-care, usual activities, pain/discomfort, and anxiety/depression). Each category contains three responses choices: top (having no problems), middle (having some or moderate problems), and bottom (being unable to do/having extreme problems). The top response choice is coded as “1”, the middle response choice as “2”, and the bottom response choice as “3”; while ambiguous values (e.g. multiple boxes ticked for one category) are treated as missing values, which are coded as “9”. As a result, a person's health status can be defined by a 5-digit number, ranging from 11111 (having no problems in all dimensions) to 33333 (having extreme problems in all dimensions). For example, 12321 indicates having no problems in mobility and anxiety/depression, having slight problems in self-care and pain/discomfort, and having extreme problems in usual activities. Thus, there are potentially 243 ( $=3^5$ ) different health states.

Visual analogue scale (VAS) is the second part of the questionnaire, asking to mark health status on the day of the interview on a 20 cm vertical scale with end points of 0 and 100. There are notes at the both ends of the scale that the bottom rate (0) corresponds to “the worst health you can imagine”, and the highest rate (100) corresponds to “the best health you can imagine”. The respondents have to draw a line from the box on the questionnaire to the scale indicates the health state of the interviewed day; while ambiguous values (e.g. the line crosses the VAS twice) should be treated as missing values, which are coded as “999”. Eventually, the EQ-5D-3L results can be converted into a single index value; many different terms are in use for these index values, such as preference weights, preference-based values, utilities, QALY weights, etc.

### **Work Productivity and Activity Impairment (WPAI)**

WPAI outcomes are expressed as impairment percentages, with higher numbers indicating greater impairment and less productivity (i.e., worse outcomes) as follows:

#### **Questions**

Q1 = currently employed

Q2 = hours missed due to specified problem

Q3 = hours missed other reasons

Q4 = hours actually worked

Q5 = degree problem affected productivity while working

Q6 = degree problem affected regular activities

### **Scores**

Multiply scores by 100 to express in percentages.

- Percent work time missed due to problem

$$Q2 / (Q2+Q4)$$

- Percent impairment while working due to problem

$$Q5 / 10$$

- Percent overall work impairment due to problem

$$Q2/(Q2+Q4)+[(1-Q2/(Q2+Q4) \times (Q5/10)]$$

- Percent activity impairment due to problem

$$Q6 / 10$$

### **Patient Treatment Satisfaction Questions**

The patient treatment satisfaction questions were developed de novo for this study and are not considered “validated” questions. There are totally 4 questions asking about the patients’ satisfaction with the following 4 aspects respectively:

1. The way RA treatment improves the morning stiffness in and around the joints.
2. The way RA treatment improves the mobility.
3. The way RA treatment improves the ability to perform daily living requiring fine motor skills.
4. The overall RA treatment.

There are totally 5 responses for each of the question: very satisfied, somewhat satisfied, neither satisfied nor dissatisfied, somewhat dissatisfied, and very dissatisfied.

#### **3.5.2      *Exposure/Independent Variables of Interest***

- **Patient demographics (if data available)**

- Date of birth
- Age at baseline
- Age groups
- Gender at birth
- Marital status (married, unmarried)
- Medical plan type
  - ✓ The type of healthcare plan each patient is enrolled in at baseline will be determined, including National/Public insurance, Private insurance, Employer benefits, and Other

- **Clinical characteristics**

- Initial Diagnosis of Rheumatoid Arthritis (RA)
  - ✓ Year of initial diagnose
- Initiation of Adalimumab
  - ✓ First time administration (DD/MM/YYYY)
  - ✓ Dosage of first injection (in mg)
- Disease status of RA
  - ✓ Moderate (defined as Disease Activity Score in 28 Joints (DAS28) between 3.2 and 5.1)
  - ✓ Severe (DAS28>5.1)
- Erythrocyte sedimentation rate (ESR) (in mm/hour)
- C reactive protein (CRP) (in mg/L)
- Disease Activity Score in 28 joints (DAS28)

To calculate the DAS28, the physician or specialist nurse will:

1. Count the number of swollen joints (out of the 28)
2. Count the number of tender joints (out of the 28)
3. Take blood to measure the erythrocyte sedimentation rate (ESR) or C reactive protein (CRP); the latest measurement in the medical records may also be used if a blood draw is not standard for that visit
4. Ask the patient to make a ‘global assessment of health’ which will be indicated by marking a 10 cm line between very good and very bad

The physician or specialist nurse will then mark each component score on the CRF and the DAS28 score if calculated (an online scoring calculator for the DAS28 can be found at <http://www.das-score.nl/das28/DAScalculators/dascalculators.html>).

The DAS28 will be scored using the following formula:

$$\text{DAS28} = 0.56 * \text{sqrt}(\text{tender28}) + 0.28 * \text{sqrt}(\text{swollen28}) + 0.70 * \ln(\text{ESR or CRP}) + 0.014 * (\text{Global assessment of Health})$$

DAS28 scores will be interpreted using the following categorization:

- ✓ Remission: DAS28  $\leq$  2.6
- ✓ Low Disease Activity:  $2.6 < \text{DAS28} \leq 3.2$
- ✓ Moderate Disease Activity:  $3.2 < \text{DAS28} \leq 5.1$
- ✓ High Disease Activity: DAS28  $> 5.1$
- comorbidities
  - ✓ Myocardial infarction
  - ✓ Congestive heart failure
  - ✓ Peripheral vascular disease
  - ✓ Cerebrovascular disease
  - ✓ Dementia
  - ✓ Chronic pulmonary disease
  - ✓ Connective tissue disease
  - ✓ Ulcer disease
  - ✓ Mild liver disease
  - ✓ Diabetes
  - ✓ Hemiplegia
  - ✓ Moderate or severe renal disease
  - ✓ Diabetes with end-organ damage
  - ✓ Any tumor
  - ✓ Leukemia
  - ✓ Lymphoma
  - ✓ Moderate or severe liver disease
  - ✓ Metastatic solid tumor
  - ✓ AIDS

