9.2.4.7 Study Documents

Clinical case report form (CRF)

The clinical CRF will document the patient's current status (moderate, severe RA), Disease Activity Score in 28 joints (DAS28), prior and current treatments and other relevant clinical and demographic data to be used in segmenting the population during analysis.

To calculate the DAS28 the physician or specialist nurse will:

1. Count the number of swollen joints (out of the 28)
2. Count the number of tender joints (out of the 28)
3. Take blood to measure the erythrocyte sedimentation rate (ESR) or C reactive protein (CRP); the latest measurement in the medical records may also be used if a blood draw is not standard for that visit
4. Ask the patient to make a 'global assessment of health' which will be indicated by marking a 10 cm line between very good and very bad

The physician or specialist nurse will then mark each component score on the CRF and the DAS28 score if calculated (an online scoring calculator for the DAS28 can be found at <http://www.das-score.nl/das28/DAScalculators/dascalculators.html>).

The DAS28 will be scored using the following formula:

$$\text{DAS28 ESR} = 0.56 * \text{sqrt}(\text{tender28}) + 0.28 * \text{sqrt}(\text{swollen28}) + 0.70 * \ln(\text{ESR}) + 0.014 * (\text{Global assessment of Health in cm})$$

$$\text{DAS28 CRP} = 0.56 * \text{sqrt}(\text{tender28}) + 0.28 * \text{sqrt}(\text{swollen28}) + 0.36 * \ln(\text{CRP}) + 0.014 * (\text{Global assessment of Health in cm}) + 0.96$$

DAS28 scores will be interpreted using the following categorization:

- Remission: DAS28 \leq 2.6
- Low Disease activity: $2.6 < \text{DAS28} \leq 3.2$
- Moderate Disease Activity: $3.2 < \text{DAS28} \leq 5.1$
- High Disease Activity: DAS28 > 5.1

The full CRF is presented in Appendix C.

PRO questionnaires

The following PRO questionnaires will be included in the patient questionnaire packet.

Health Assessment Questionnaire Disability Index (HAQ DI)

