Appendix C. Clinical Case Report Form (CRF)

Baseline:

1023259 Real-World Impact of RA
____ - ____
Site number Participant ID

Clinician Case Report Form (Baseline)

All of the following information must be completed by the clinician or his/her representative.

Clinician name: _____

Clinician signature: _____

[figure not shown]
Patient ID	

____	____	

Site #	Participant #	

	____	____	Site #	Participant #														
____	____																		
Site #	Participant #																		
Today's date	

____	____	/	____	____	/	____	____	____	

Day	Month		Year						

	____	____	/	____	____	/	____	____	____	Day	Month		Year					
____	____	/	____	____	/	____	____	____											
Day	Month		Year																

Please provide the information below.

1. When was the patient diagnosed with Rheumatoid Arthritis?	

____	____	____	____	

Year	

	____	____	____	____	Year			
____	____	____	____						
Year									
2. What is the patient's current disease status?	 Moderate  Severe								

1023259 Real-World Impact of RA
 -
 Site number Participant ID

imshealth™
 INTELLIGENCE APPLIED.

Please provide the information below.		
3. Please perform a swollen and tender joint examination on your patient using the figure below and record the total number of tender/swollen joints in the appropriate boxes on the right.	  Tender Joint Count	  Swollen Joint Count
If diagnosis is RA:		
4. Please record the most recent Erythrocyte Sedimentation Rate (ESR) (in mm/hour) or C-reactive protein (CRP) (in mg/L) of this patient.	  ESR (mm/hour) Test Date (DD/MM/YYYY): ____/____/_____	
	  CRP (mg/L) Test Date (DD/MM/YYYY): ____/____/_____	
5. Please record the latest DAS28 score*, if calculated		

* For calculation instruction, please refer to study protocol, page 21, clinical case report form (CRF).

1023259	Real-World Impact of RA
Site number	Participant ID

6. Please check all the comorbidities this patient has currently.

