**DOCUMENT HISTORY**

Version #	Issue Date	Author/Editor	Sections Changed	Change Summary
V0.2	2 Jan, 2018	[REDACTED]	Section	
 
1. Patient's impression of change in RA at weeks 12 and 24 after the initiation of adalimumab has been added in the Study Objectives and Statistical Analysis Section according to Taiwan protocol.
 
2. Disease status of RA (moderate, severe, missing) has been deleted in Table 2, since it's duplicated with DAS28 categorization.
 
3. Dosage of first adalimumab injection has been deleted in Table 2, since the DOSE should be 40MG for all adults.
 

V0.1	8 Aug, 2017	[REDACTED]	All	Initial Version

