## 5.2 Analysis Plan for Demographic and Clinical Characteristics

- Descriptive statistics will be presented for patient demographics (Excel Table 1), and clinical characteristics (Excel Table 2) for all patients by country. The following measures will be assessed as of the patient's baseline:
  - Patient age (mean, SD, minimum, maximum, median; categories: 18-34, 35-44, 45-54, 55-64, 65-74, 75+, missing)
  - Gender (male, female, missing)
  - Marital status (married, unmarried, missing)
  - Medical insurance type (National/Public insurance, Private insurance, Employer benefits, other, no insurance, missing)
  - Disease Activity Score in 28 joints - DAS28 (mean, SD, minimum, maximum, median; categories: Remission, Low Disease Activity, Moderate Disease Activity, High Disease Activity, Missing)
  - Number of patients with each of the comorbidities at baseline visit (See 3.5.2), and number of patients with any of these comorbidities

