#### **5.5 Analysis Plan for Additional Secondary Objectives**

- Descriptive statistics will be presented for post-index overall RA related direct healthcare resource utilization (Excel Table 8)

- Consultations/visits to healthcare professionals for treatment of RA (number of patients with  $\geq 1$  visit; categorized by the treatment department listed in 3.5.4)
- Procedures received when visiting the healthcare professional(s) for treatment of RA (number of patients with  $\geq 1$  procedure; categories listed in 3.5.4)
- surgeries received when visiting the healthcare professional(s) for treatment of RA (number of patients with  $\geq 1$  surgery; categories listed in 3.5.4)
- Hospitalizations in relation to RA (number of patients with  $\geq 1$  admission)
- Length of stay in days (mean, SD, median)
- Concomitant medications taken for RA (number of patients with  $\geq 1$  medication; categories listed in 3.5.4))

- Associations between disease severity (measured by DAS28) and PROs (HAQ DI score, SF-36 domain scales, EQ-5D-3L index, WPAI outcomes) will be analyzed using the bivariate linear regression model (Excel Table 9.1). Separate models will be estimated to identify the association between DAS28 and each of the PROs.
- Additionally, in Excel Table 9.2, separate bivariate liner regression models will be estimated to identify the association between change in DAS28 and change in each of the PROs at 12 and 24 weeks after baseline respectively.

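### The SAP scores DAS28 from CRP with the ESR coefficient and no constant, which contradicts the protocol's DAS28-CRP formula while keeping the same cut-offs

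*SAP*

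**What the plan says.** Protocol section 9.2.4.7 scores DAS28 in two ways. The ESR formula uses 0.70 × ln(ESR) with no constant. The CRP formula replaces the marker term and adds a constant: "0.36 * \ln(\text{CRP}) + 0.014 * (\text{Global assessment of Health in cm}) + 0.96".

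SAP section 3.5.2 has a single formula covering both markers: "0.70 * \ln(\text{ESR or CRP}) + 0.014 * (\text{Global assessment of Health", with no constant. No other part of the SAP gives a CRP formula. The joint-count terms and the category cut-offs (2.6, 3.2, 5.1) are the same in both documents.

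On where the score comes from, SAP 3.5.2 says: "The physician or specialist nurse will then mark each component score on the CRF and the DAS28 score if calculated". The case report form in protocol Appendix C asks: "Please record the latest DAS28 score*, if calculated", with the footnote: "For calculation instruction, please refer to study protocol, page 21, clinical case report form (CRF".

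DAS28 is used in these analyses:
- SAP 5.2 (Table 2) reports its baseline mean and "categories: Remission, Low Disease Activity, Moderate Disease Activity, High Disease Activity, Missing".
- SAP 5.5 plans regressions for "Associations between disease severity (measured by DAS28) and PROs" (Table 9.1), and for change in DAS28 against change in each patient-reported outcome (Table 9.2).
- The SAP document history adds: "Disease status of RA (moderate, severe, missing) has been deleted in Table 2", because that row was thought to duplicate the DAS28 categories.

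**The concern.** The SAP names CRP explicitly, so this is not an ESR-only formula being read too widely. CRP scoring is also a planned route: eligibility and the schedule of events accept either marker, and the form has a CRP field in mg/L. Both texts are current; Amendment 01 changed only the sample size and the milestones.

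A programmer who follows the SAP for a CRP-scored patient gets a number that is not on the protocol's scale and then applies the protocol's cut-offs to it. Patients who entered with DAS28 above 3.2 could appear in Table 2 as low activity or in remission. Those categories are the only severity breakdown that SAP 5.2 lists for that table. Tables 9.1 and 9.2 would regress outcomes on a variable whose CRP component is overweighted. If sites score by the protocol and blanks are filled by the SAP rule, one variable would hold two scales.

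**Working it through.** **Inputs.** Protocol CRP marker part: 0.36 × ln(CRP) + 0.96 (section 9.2.4.7). SAP marker part: 0.70 × ln(CRP) (section 3.5.2). CRP in mg/L (SAP 3.5.2 and the case report form). Cut-offs 2.6 / 3.2 / 5.1 (both documents). The CRP values and patient profiles below are illustrative assumptions. The plan gives no figure of its own to reproduce.

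**Level.** With the same joint counts and the same global assessment in the same unit:

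SAP − protocol = 0.70 × ln(CRP) − [0.36 × ln(CRP) + 0.96] = 0.34 × ln(CRP) − 0.96.

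This is zero only at CRP = exp(0.96 / 0.34) = 16.84 mg/L.

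**Category.** A SAP score sits on a cut-off when the protocol score equals that cut-off + 0.96 − 0.34 × ln(CRP).

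| CRP (mg/L) | SAP − protocol | Protocol score at which the SAP score equals 2.6 / 3.2 / 5.1 |
|---|---|---|
| 1 | −0.96 | 3.56 / 4.16 / 6.06 |
| 3 | −0.59 | 3.19 / 3.79 / 5.69 |
| 5 | −0.41 | 3.01 / 3.61 / 5.51 |
| 10 | −0.18 | 2.78 / 3.38 / 5.28 |
| 16.8 | 0 | 2.60 / 3.20 / 5.10 |
| 30 | +0.20 | 2.40 / 3.00 / 4.90 |
| 50 | +0.37 | 2.23 / 2.83 / 4.73 |

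For patients above the entry threshold of 3.2:
- CRP 5: protocol scores above 3.2 and up to 3.61 become low activity; those above 5.1 and up to 5.51 become moderate.
- CRP 1: scores above 3.2 and up to 3.56 become remission; those above 3.56 and up to 4.16 become low.
- CRP 50: scores above 4.73 and up to 5.1 move up to high.
- Falling from above 3.2 to remission needs a downward shift of more than 0.6, so CRP below exp(0.36 / 0.34), about 2.9 mg/L.

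**Worked profiles** (global assessment in cm).
- Tender 6, swollen 5, global 5: 0.56 × √6 + 0.28 × √5 + 0.014 × 5 = 2.068. At CRP 3 the protocol gives 2.068 + 0.36 × ln 3 + 0.96 = 3.42 (moderate) and the SAP gives 2.068 + 0.70 × ln 3 = 2.84 (low).
- The same patient at CRP 15: 4.00 against 3.96, both moderate.
- Tender 9, swollen 8, CRP 60, global 6: 4.99 (moderate) against 5.42 (high).

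**Change.** The 0.96 cancels, but the CRP part is weighted 0.70 / 0.36 = 1.94 times. A fall in CRP from 20 to 2 contributes 0.36 × ln 10 = 0.83 points under the protocol and 0.70 × ln 10 = 1.61 under the SAP. If CRP does not change, the two agree.

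**Unit of the global assessment.** The protocol formula says cm; the SAP formula gives no unit, although its text describes a 10 cm line. The term is at most 0.014 × 10 = 0.14 in cm. Neither document mentions millimetres here; if, as an assumption, the mark were entered in mm, the maximum would be 0.014 × 100 = 1.40. The shift above does not depend on the unit as long as both formulas use the same one.

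**The case against.** The strongest reply is that the SAP formula may never be run. It stands below an instruction to site staff, DAS28 is absent from the derived variables in SAP 3.5.4, and the form sends sites to the protocol for the calculation. The readable text of the form shows no labelled field for the global assessment, though one may sit in a figure not shown; without that item, central derivation is impossible. SAP 3.5.5 also rules out general imputation, and Table 2 has a missing category, so blank scores may simply stay blank. If only site scores computed by the protocol formula are analysed, the conflict has no effect.

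This makes the harmful route less certain but does not close it. SAP 3.5.2 states the formula as the way DAS28 is to be scored, and computing a score from recorded components is not strictly imputation. The form asks for a score only if one was calculated, so blanks are to be expected. Both documents also point sites to an online calculator whose formula cannot be seen here, so site scores are not guaranteed to follow the protocol either.

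Two limits stand. Category bands below 3.2 matter little in a baseline table of patients enrolled above 3.2. The analyses exposed are descriptive, associative, sensitivity or exploratory.

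**Conclusion.** The conflict is real and should be fixed. For CRP-based scores the SAP rule moves the level by 0.34 × ln(CRP) − 0.96, almost doubles the weight of CRP change, and reclassifies patients near a cut-off, downward below 16.8 mg/L and upward above it.

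This matters only if some patients are scored with CRP and their scores are derived by the SAP rule. The documents give neither the share of CRP-scored patients, which may be zero, nor the CRP distribution, so the number reclassified cannot be computed.

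Tables 2, 9.1 and 9.2 are exposed. The HAQ DI sensitivity ANOVA (SAP 5.3) and the modifier models (SAP 5.6, Table 10) are affected only if baseline severity there is based on DAS28. SAP 3.5.2 and 5.5 point that way, but the form also records a clinician-rated status. No listed table reports mean DAS28 change. ESR-based scores (with the same unit for the global assessment), the primary paired t-test and the HAQ DI responder counts are unaffected.

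**What to change.** - Replace the formula in SAP 3.5.2 with separate ESR and CRP formulas that match protocol 9.2.4.7.
- Before coding, confirm the unit of the global assessment and state it in both documents.
- State whether the site-recorded or the derived DAS28 is analysed, and whether a blank site score is computed from its components or left missing. If scores are derived, name the field that holds the global assessment.
- Flag the marker used for the score at each visit.
- State whether baseline severity in the ANOVA and Table 10 is DAS28-based or the clinician-rated status.
- Optionally, require the same marker at both visits for change scores; neither document asks for this.

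The cost is SAP wording, a few lines of derivation code and one flag. ESR, CRP and joint counts are already on the form, so no new data are needed. If the global assessment is not in the database, central derivation is not possible; site-recorded scores must then be used, and blanks stay missing.
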